Study Title	Study to optimize and validate the treatment parameters for the Empower Neuromodulation System
Study & Revision Number	CRD-12-1154 Rev 1
Device	Empower Neuromodulation System
Objectives	
 1. Compare two active treatment electrode locations to evaluate the effect of electrode placement on the appearance of sensory nerve action potentials (SNAPs). The appearance of SNAPs indicates effective sensory nerve stimulation. 2. Evaluate the usability of each of the two active treatment electrode locations (via the System Usability Survey (SUS)). 3. For one sham treatment electrode location (i.e. Sham #1), evaluate subject blinding, i.e. does the subject believe it is the active or sham treatment. 4. Compare two sham treatment electrode locations to confirm that the sham locations do not induce SNAPs.
Indications for Use/Subject Population	
After initial development, we will propose that the Empower Neuromodulation System is indicated for the treatment of alcohol use disorder (AUD). Per the inclusion criteria of this pilot study, enrollment in this study is not restricted to only subjects with AUD.
 
The subject population is adult males or females age 21-75 years old.

Study Design	Pilot feasibility study to optimize and validate treatment parameters.
Number of Subjects	Up to 40
Number of Sites	One (1)
Study Procedures Outline	
 1. Screening and ICF 2. Breath alcohol test 3. Eligibility review 4. The subject will be administered a 5-minute treatment at a sham treatment location and then be asked if he/she believes it is the active treatment, sham treatment, or does not know. 5. Sensory nerve action potential (SNAP) assessment. A clinical-grade nerve conduction assessment system (UltraPro 1000, Natus, Inc.) will be used both to provide electrical stimulation at each of four locations (two potential active treatment sites and two potential sham treatment sites) and to record SNAPs during stimulation. The appearance of SNAPs are an indication of sensory nerve stimulation. 6. The subject will self-administer a 10-minute treatment session at one active treatment site. After a 5-minute break, the subject will self-administer a 10-minute treatment session at the other active treatment site. After each

	
treatment session, the subject will complete two usability surveys about the treatment.
 
7. Subject compensation

Inclusion Criteria	
 1. Is 21-75 years old 2. Can provide informed consent 3. Currently has a stable living situation 4. Had one heavy drinking week (>7 drinks/week for women; >14 drinks/week for men) over the past 6 months 5. Has a breath alcohol concentration of 0.00% at enrollment 6. Is willing to follow all study procedures
Exclusion Criteria	
 1. Has been diagnosed with schizophrenia, epilepsy, peripheral neuropathy, or nerve damage 2. Has implanted electrical and/or neurostimulator device (e.g. pacemaker, defibrillator, vagal neurostimulator, deep brain stimulator, spinal stimulator, sacral stimulator, bone growth stimulator, or cochlear implant) 3. Has a tattoo or conductive, ferromagnetic, or other magnetic-sensitive metals that cannot be removed from the skin at the electrode sites 4. Is currently pregnant or breastfeeding 5. Has a bleeding disorder, a history of deep vein thrombosis, or is on anticoagulation drugs 6. Has used an investigational drug/device therapy within the past 4 weeks 7. Is deemed unsuitable for enrollment in study by the PI
Safety	Adverse Events will be recorded and reported appropriately throughout the study.
Sample Size Calculations	For the two active treatment sites, the percent of subjects who experience effective stimulation of the nerve via SNAP assessment will be compared via a two-proportion z-test ($p \leq 0.05$ for statistical significance).

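### Does the unstated handling of 'does not know' answers leave the Sham #1 blinding result open to choice?

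*Combined protocol and SAP*

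**What the plan says.** All references are to the combined protocol and SAP.

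- **Objectives, item 3** limits the blinding question to one location, "For one sham treatment electrode location (i.e. Sham #1"), and states its aim as to "evaluate subject blinding, i.e. does the subject believe it is the active or sham treatment".
- **Study Procedures Outline, step 4** gives the sham session and the question that follows it: the subject will "then be asked if he/she believes it is the active treatment, sham treatment, or does not know". Three answers are therefore allowed.
- **Study Procedures Outline, step 6** has subjects complete usability surveys after each active session. It lists no belief question there.
- **Sample Size Calculations** holds the only analysis statement: "For the two active treatment sites, the percent of subjects who experience effective stimulation of the nerve via SNAP assessment will be compared", by a two-proportion z-test. The guesses from step 4 are not mentioned.
- **Study Design** describes a "Pilot feasibility study to optimize and validate treatment parameters". **Number of Subjects** sets a ceiling of 40.

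**The concern.** Objective 3 reads as a two-way question, while the data have three categories. A reader who wants one number for Objective 3 must decide what to do with 'does not know'. It can stay in the denominator, be dropped, or count as a failure to identify the sham. The plan does not choose among these, and it does not say which figure is the result.

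The choice could matter. The same answers might be reported as fewer than half the subjects believing Sham #1 was active, or as three-quarters failing to recognise it as sham. If the choice were made after the data were seen, the more flattering figure could be put forward. Objective 3 is one of four numbered objectives, so it is reasonable to ask whether its summary should be settled in advance.

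**Working it through.** **Plan's own figure.** There is none to reproduce. The documents give no expected proportion, threshold, power or sample size for Objective 3.

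**Inputs.** From the documents: three answer categories (step 4) and at most 40 subjects (Number of Subjects). Assumed for illustration: A = 18 active, S = 10 sham, D = 12 'does not know', n = 40. Both the 30% 'does not know' share and the 18:10 split are assumptions.

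**The three readings, with exact (Clopper-Pearson) 95% intervals.**

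| Reading | Formula | Result | 95% CI |
|---|---|---|---|
| Active among all | A/n = 18/40 | 45.0% | 29.3 to 61.5 |
| Active among those who chose | A/(A+S) = 18/28 | 64.3% | 44.1 to 81.4 |
| Did not identify sham | (A+D)/n = 30/40 | 75.0% | 58.8 to 87.3 |

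**Size of the gap.** (A+D)/n − A/n = D/n. Here 75% − 45% = 30 points = 12/40. The identity holds for any counts, so the spread is exactly the 'does not know' share and is zero if nobody gives that answer.

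**Sensitivity to the assumed counts (n = 40).**

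| A | S | D | A/n | A/(A+S) | (A+D)/n |
|---|---|---|---|---|---|
| 14 | 14 | 12 | 35.0% | 50.0% | 65.0% |
| 18 | 10 | 12 | 45.0% | 64.3% | 75.0% |
| 21 | 7 | 12 | 52.5% | 75.0% | 82.5% |
| 23 | 13 | 4 | 57.5% | 63.9% | 67.5% |
| 36 | 2 | 2 | 90.0% | 94.7% | 95.0% |

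The 30% alone does not fix the three figures; the split among those who chose matters too. When few answer 'does not know', the three readings nearly coincide.

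**Do Objective 3 and step 4 conflict?** The objective states what is being evaluated, and the step lists the answers a subject may give. 'Does not know' is an ordinary answer to whether a treatment was active or sham. The two places fit together; what is missing is a reporting convention.

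**Does any rule in the plan turn on the choice?** No cut-off is set for Objective 3, at 50% or anywhere else, so crossing such a line has no consequence under the plan. No belief question follows the active sessions in step 6, so there is no active-versus-sham contrast of guesses that a choice of denominator could distort.

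**What does a plain tabulation give?** Reporting A, S and D over all subjects who had the sham session prints 45%, 25% and 30% in the example. The 75% is 100% − 25%, and the 64.3% is 45/(45 + 25). All three readings are visible from one line of counts.

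**The case for a change.** The strongest case for a change is that the ambiguity is built in. Any non-zero 'does not know' share separates the readings, whatever the assumed counts. One sentence in the analysis text would prevent selective reporting, at no cost in subjects or procedures. In a study meant partly to validate parameters, 45% and 75% could support different impressions of the same sham location.

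Much of this stands. The omission is real, the identity is exact, and writing down a convention would do no harm.

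It does not amount to a fault in the plan. No stated rule, figure or test is wrong, and none would give a wrong answer if followed as written. Different impressions become different conclusions only through a decision rule, and the plan has none for Objective 3. The natural remedy, reporting all three counts with 'does not know' in the denominator, is what a competent analyst would do with a three-option question in a pilot, so requiring it adds little. Objectives 2 and 4 also have no stated analysis. The silence on Objective 3 is part of the brevity of a synopsis and is not peculiar to the blinding question.

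Precision matters as well. Even with 40 subjects, the interval for 18/40 spans 61.5 − 29.3 = 32.2 points, about as wide as the 30-point gap between the extreme readings. That does not excuse choosing a reading after the fact. It does show that any single percentage here can only be descriptive.

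**Conclusion.** No change is needed. The plan leaves a reporting detail unstated, and analysts can fill it sensibly by tabulating the three recorded answers over everyone who completed the sham session. At the assumed 30% 'does not know' share the readings differ by up to 30 points; at 2 of 40 they differ by 5 points (90% to 95%). The documents give no way to tell which is nearer the truth.

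This conclusion rests on two things: Objective 3 stays descriptive, as the absence of any threshold or test implies, and the three counts are reported instead of a single derived percentage. If a report gave only one percentage without the counts, the reader should ask for the 'does not know' number before interpreting it.

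### The only named test, a two-proportion z-test, treats the two active sites as independent samples, but every subject is stimulated at both

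*Combined protocol and SAP*

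**What the plan says.** Objective 1 is to "Compare two active treatment electrode locations to evaluate the effect of electrode placement on the appearance of sensory nerve action potentials (SNAPs"). The outcome is binary for each subject and site: "The appearance of SNAPs indicates effective sensory nerve stimulation".

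Step 5 of the Study Procedures Outline uses one nerve conduction system "to provide electrical stimulation at each of four locations (two potential active treatment sites and two potential sham treatment sites") and records SNAPs during stimulation. No randomisation or division of subjects between the active sites is described. Step 6 also takes each subject through both active sites ("After a 5-minute break, the subject will self-administer a 10-minute treatment session at the other active treatment site"), but those sessions feed the usability surveys. The pairing of the SNAP outcome rests on step 5.

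The analysis is given only under Sample Size Calculations: "the percent of subjects who experience effective stimulation of the nerve via SNAP assessment will be compared via a two-proportion z-test", with significance at p ≤ 0.05. No other test, and no paired method, appears. The enrolment cap is 40.

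**The concern.** The two-proportion z-test is built for two separate groups of people. Here the same people supply both percentages. A subject whose nerve responds readily at one site may well respond at the other. The z-test's standard error has no term for that dependence, and its p-value is the same however the responses pair up within subjects.

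At stake is the only inferential statement in the plan. If responses are positively correlated, the test is too cautious and can miss a real difference between electrode placements in a study of at most 40 people. If they are negatively correlated, it rejects too often. The SNAP percentages themselves are not affected; the p-value and any interval are.

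**Working it through.** **Inputs from the plan.** Up to 40 subjects, hence up to 40 pairs; significance at p ≤ 0.05; binary SNAP result at each active site.

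**Inputs not in the plan, so assumed.** Two-sided testing, SNAP rates at each site, and within-subject correlation (rho). Power and effect size are also absent, so the cap of 40 cannot be reproduced from anything stated.

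**Step 1: what the z-test leaves out.** With n subjects and p̄ the average of the two site proportions,

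z = (p1 − p2) / √[2·p̄(1 − p̄)/n].

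With a common rate p at both sites, the true variance of the paired difference is 2p(1 − p)(1 − rho)/n. The statistic therefore has standard deviation √(1 − rho), not 1, and its large-sample type I error is 2[1 − Φ(1.96/√(1 − rho))]:

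- rho −0.2: 1.96/√1.2 = 1.789, error 0.074
- rho 0: 1.960, error 0.050
- rho 0.3: 1.96/√0.7 = 2.343, error 0.019
- rho 0.5: 1.96/√0.5 = 2.772, error 0.006

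**Step 2: exact check at 40 pairs.** Full enumeration of the paired 2x2 table, with P(SNAP at both) = pA·pB + rho·√[pA(1 − pA)pB(1 − pB)], gives this z-test type I error:

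| Rate at both sites | rho 0 | rho 0.1 | rho 0.3 | rho 0.5 |
|---|---|---|---|---|
| 70% | 0.048 | 0.038 | 0.019 | 0.006 |
| 95% | 0.043 | 0.033 | 0.016 | 0.005 |

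At 80% and rho −0.2 it is 0.074.

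For the paired tests, over every n from 20 to 40 and discordance probabilities up to 0.65, the maximum type I error is 0.054 for asymptotic McNemar (no continuity correction), 0.049 for mid-p and 0.030 for exact.

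**Step 3: power at 40 pairs** (same enumeration).

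| Rates | rho | z-test | Asymptotic McNemar | Mid-p McNemar |
|---|---|---|---|---|
| 80% vs 60% | 0 | 0.50 | 0.50 | 0.48 |
| 80% vs 60% | 0.3 | 0.496 | 0.625 | 0.624 |
| 80% vs 60% | 0.5 | 0.49 | 0.80 | 0.79 |
| 98% vs 85% | 0 | 0.632 | 0.577 | 0.509 |
| 98% vs 85% | 0.3 | 0.640 | 0.751 | 0.595 |

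**Step 4: one pair of totals, several answers.** Take 32/40 against 24/40. Then p̄ = 56/80 = 0.70, the standard error is √(2 × 0.70 × 0.30/40) = 0.1025, z = 0.20/0.1025 = 1.952 and p = 0.051, whatever the pairing. The unpaired Newcombe interval is −0.1 to 38.1 points. McNemar uses only b and c, the subjects with a SNAP at one site but not the other: (b − c)/√(b + c).

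| b:c | Statistic | Asymptotic p | Mid-p | Paired Newcombe 95% CI (points) |
|---|---|---|---|---|
| 8:0 | 8/√8 = 2.83 | 0.005 | 0.004 | 6.5 to 32.9 |
| 10:2 | 8/√12 = 2.31 | 0.021 | 0.022 | 3.1 to 35.5 |
| 12:4 | 8/√16 = 2.00 | 0.046 | 0.049 | 0.3 to 37.8 |
| 16:8 | 8/√24 = 1.63 | 0.102 | 0.108 | −3.8 to 41.1 |

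The sample correlations are 0.61, 0.36, 0.10 and −0.41. The last row is an extreme case that shows the direction under negative correlation.

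**The case against.** The best defence is that little hangs on this p-value. The plan calls itself a "Pilot feasibility study to optimize and validate treatment parameters" and sets no power target or decision rule. The paired data will exist, so a paired reanalysis remains possible. Positive correlation is plausible for two sites in one person, and it makes the z-test conservative. The inflated error rates need a negative correlation that nothing in the plan suggests. All of that stands, and it limits the severity.

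The remedy is not free of trade-offs either:

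- At zero or weak correlation a paired test can lose power. Over rates of 50–98%, differences of at least 6 points and 20, 30 or 40 pairs, asymptotic McNemar loses at most 0.064 at rho 0 and 0.02 at rho 0.1.
- Mid-p loses more, and not only at very high rates. At rho 0 and 40 pairs it falls below the z-test in 249 of 250 combinations, by up to 0.136, although many of the losses are small.
- The McNemar version can itself decide the result. For 40/40 against 36/40 the only possible pairing is 4:0, which gives z-test p = 0.040, asymptotic McNemar 0.046 and mid-p 0.0625.
- Conservatism is a statement about error rates, not about every dataset. For 39/40 against 34/40 with a 5:0 split, the z-test gives 0.048 and exact McNemar 0.0625.

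These points argue for naming one paired version in advance. They do not make an independent-samples test suitable for paired data. Leaving the choice until after the data are seen is the weakest option, because the same totals can fall on either side of 0.05.

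**Conclusion.** The concern holds. The mismatch between step 5 and the named test follows from the plan's own text and needs no assumed number. Its direction and size depend on a correlation the plan does not give. Across the assumed correlations from 0 to 0.5, at 70% SNAPs and 40 pairs, the nominal 0.05 test runs at 0.048 down to 0.006. The accompanying power loss for 80% against 60% ranges from nothing to about 0.31 (0.80 − 0.49). With positive correlation the main risk is a missed difference between sites. This should be fixed, but in a pilot with no decision rule tied to the p-value it is of moderate weight.

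**What to change.** In Sample Size Calculations, replace the two-proportion z-test with a two-sided McNemar test on each subject's pair of results (SNAP yes/no at active site 1 and at active site 2), significant at p ≤ 0.05. Name the version before data are seen. The asymptotic form without continuity correction did not fall below the z-test in power at rho 0.2 to 0.5 on the grid above, at the price of a type I error of up to 0.054. Mid-p keeps the error below 0.05 but gives up power at weak correlation, in small samples and near the ceiling. Exact McNemar is the most conservative.

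Report the paired 2x2 table (both sites, site 1 only, site 2 only, neither) and the difference in SNAP rates with a 95% interval for matched proportions (Tango or paired Newcombe). The cost is a sentence or two of analysis wording, with no extra subjects, procedures or data.

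### Does comparing the two active sites only on SNAP present or absent leave the trial unable to answer its question about electrode placement?

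*Combined protocol and SAP*

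**What the plan says.** Objectives, item 1, is to "Compare two active treatment electrode locations to evaluate the effect of electrode placement on the appearance of sensory nerve action potentials (SNAPs"). The sentence that follows gives the criterion: "The appearance of SNAPs indicates effective sensory nerve stimulation". Item 2 covers a different aspect of the same two sites: "Evaluate the usability of each of the two active treatment electrode locations (via the System Usability Survey (SUS").

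Study Procedures Outline, step 5, uses a clinical nerve conduction system "to provide electrical stimulation at each of four locations (two potential active treatment sites and two potential sham treatment sites"). The same system also serves "to record SNAPs during stimulation". Both active sites are therefore assessed in each subject. In step 6 the subject self-administers a treatment session at each active site and completes two usability surveys after each.

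Sample Size Calculations names one test: "the percent of subjects who experience effective stimulation of the nerve via SNAP assessment will be compared via a two-proportion z-test", with significance at p ≤ 0.05. Number of Subjects gives a maximum of 40. The protocol states no expected response rates, target power or effect size, and names no amplitude, latency or threshold variable. Study Design reads "Pilot feasibility study to optimize and validate treatment parameters".

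**The concern.** A nerve conduction system records a waveform, and the plan reduces it to yes or no. If both placements produce a SNAP in nearly every subject, the two percentages will be close to each other and to 100%, and the test cannot show whether one placement gives a larger response. The exclusion of diagnosed peripheral neuropathy and nerve damage makes high response rates at both sites plausible. For a study whose aim includes optimizing parameters, this looks like discarding the most informative part of the recording, and the choice of site would then rest on the usability surveys. An amplitude comparison within subjects seems cheap to add because the recordings are made anyway.

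**Working it through.** **1. Question against analysis**

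| Element | Where | Content |
|---|---|---|
| Question | Objectives, item 1 | Effect of placement on whether SNAPs appear |
| Criterion | Objectives, item 1, second sentence | Appearance means effective sensory nerve stimulation |
| Measurement | Study Procedures Outline, step 5 | SNAPs recorded at both active sites in each subject |
| Analysis | Sample Size Calculations | Percent of subjects with effective stimulation, site against site |

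The outcome is the same in every row. No row refers to response size.

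**2. What the binary test can detect**

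The plan has no power figure to reproduce. Inputs from the protocol are 40 observations per site (the maximum) and α = 0.05. Two-sided testing and all response rates are assumptions. With p̄ the mean of the two rates:

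power ≈ Φ{ [ |p1 − p2| − 1.96·√(2p̄(1 − p̄)/n) ] / √[(p1(1 − p1) + p2(1 − p2))/n] }

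For 95% against 85%, p̄ = 0.90:
- null standard error: √(2 × 0.90 × 0.10/40) = 0.0671
- alternative standard error: √[(0.0475 + 0.1275)/40] = 0.0661
- power: Φ[(0.10 − 0.1315)/0.0661] = Φ(−0.476) = 0.32

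Exact binomial enumeration of the same test gives:

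| Assumed rates | Exact power |
|---|---|
| 95% vs 85% | 0.35 |
| 90% vs 80% | 0.25 |
| 95% vs 75% | 0.76 |
| 95% vs 73% | 0.82 |

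These values treat the sites as independent. Allowing a latent within-subject correlation of up to 0.5 moves the first three to 0.33, 0.21 and 0.79.

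In terms of counts, suppose 38/40 respond at one site:
- 32/40 at the other: pooled proportion 70/80 = 0.875, standard error √(0.875 × 0.125 × 2/40) = 0.0740, z = 0.15/0.0740 = 2.03, significant
- 33/40 at the other: pooled proportion 71/80 = 0.8875, standard error 0.0707, z = 0.125/0.0707 = 1.77, not significant

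Large differences are detectable and 10-point differences mostly are not. This follows from the sample size and contradicts nothing the plan states.

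**3. Both sites near 100%**

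With both true rates at 98%, the z-test rejects in under 1% of trials. That is not low power: the rates are equal, so the null hypothesis is true and the figure is a type I error rate. It cannot be set beside the power of an amplitude test, which addresses a different hypothesis.

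**4. What amplitude would add**

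Assumed model: 98% response at both sites, presence correlation 0.5, lognormal amplitude, absent = 0, Wilcoxon signed-rank test, 40 subjects. Each range is for amplitude correlation 0 to 0.5, by simulation:

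| SD of log amplitude | 20% larger at one site | 30% larger |
|---|---|---|
| 0.4 | 0.41 to 0.70 | 0.74 to 0.94 |
| 0.6 | 0.24 to 0.38 | 0.40 to 0.67 |
| 0.8 | 0.14 to 0.25 | 0.25 to 0.45 |

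The protocol gives no amplitude SD. Away from the ceiling the result depends on the mechanism. If response is a shared normal latent variable (correlation 0 to 0.5), signed-rank power is 0.73 to 0.95 for 95% vs 85% and 0.44 to 0.72 for 90% vs 80%. If placement only decides whether the nerve is reached, and amplitude among responders is equal, it is about 0.14 to 0.16 in both cases (SD 0.4), below the z-test's 0.35 and 0.25.

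**The case for a change.** The strongest case for the concern is that the recordings are already made, one exported value and one analysis line would suffice, and a rule set in advance is better than an amplitude analysis chosen after the data are seen. An estimate with its confidence interval would describe response size, which a percentage cannot. All of that is true, and it is also true that no graded SNAP measure is named.

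It does not make the omission an error. Such an analysis would matter for choosing a site only if a larger SNAP meant a better placement, and the protocol does not say so. Its criterion is appearance. In step 5 the nerve conduction system, not the Empower device, supplies the stimulation, so amplitude would describe the response to that stimulator at whatever setting was used. The protocol does not say that stimulator setting and recording arrangement match between the active sites. Merely recording them would leave any amplitude difference confounded with those settings. As a supportive analysis that could not override the yes/no result, it would not change the answer to Objective 1 or raise the power of the planned test.

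Usability is also a planned basis for judging the two sites, under Objective 2. Relying on it when both sites stimulate the nerve is consistent with the plan.

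**Conclusion.** The concern does not hold. Objective 1, the stated criterion and the planned analysis all concern whether SNAPs appear, so the plan followed as written addresses its own question, including when both sites respond in nearly everyone. The low power for 10-point differences (about 0.21 to 0.35 under the assumed rates, with 40 subjects and two-sided α of 0.05) is a feature of a small pilot and breaches no stated figure. The benefit of an amplitude endpoint is uncertain: at ceiling, power for a 20% to 30% difference ranges from about 0.14 to 0.94 over log-SDs of 0.4 to 0.8 and amplitude correlations of 0 to 0.5, and under the all-or-none model it falls below the planned test. Adding amplitude is a reasonable preference that the sponsor may take or leave. This conclusion concerns only the choice of a yes/no outcome. Whether a z-test for independent proportions suits two sites measured in the same subjects is a separate question, and changing the test would not recover response size.
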